If a patient requires positive pressure ventilation after a period of unassisted breathing, the study ventilator procedures will resume unless the patient was discharged from the hospital or > 28 days elapsed since enrollment.

G.5 Removal from the Ventilator Management Protocol

Patients may be removed from the 6 ml / kg tidal volume ventilation requirement if they develop neurologic conditions where hypercapnia would be contraindicated (e.g., intracranial bleeding, $GCS \le 8$, cerebral edema, mass effect [midline shift on CT scan], papilledema, intracranial pressure monitoring, fixed pupils).

H Conservative Fluid Management Approach

This fluid protocol captures the primary positive outcome of the FACTT trial on increasing ventilator free days. This protocol should be initiated within four hours of randomization in enrolled patients, and continued until UAB or study day 7, whichever occurs first.

- 1. Discontinue maintenance fluids.
- 2. Continue medications and nutrition.
- 3. Manage electrolytes and blood products per usual practice.
- 4. For shock, use any combination of fluid boluses[#] and vasopressor(s) to achieve MAP ≥ 60 mmHg as fast as possible. Wean vasopressors as quickly as tolerated beginning four hours after blood pressure has stabilized.
- 5. Withhold diuretic therapy in renal failure § and until 12 hours after last fluid bolus or vasopressor given.

CVP	PAOP	MAP ≥ 60 mm Hg AND off vasopressors for ≥ 12 hours							
(recommended)	(optional)	Average urine output < 0.5 ml/kg/hr	Average urine output > 0.5 ml/kg/hr						
>8	> 12	Furosemide* Reassess in 1 hour	Furosemide*						
4-8	8-12	Give fluid bolus as fast as possible#	Reassess in 4 hours						
< 4	< 8	Reassess in 1 hour	No intervention Reassess in 4 hours						

[§] Renal failure is defined as dialysis dependence, oliguria with serum creatinine > 3mg/dl, or oliguria with serum creatinine 0-3 with urinary indices indicative of acute renal failure.

[#] Recommended fluid bolus= 15 mL / kg crystalloid (round to nearest 250 mL) or 1 Unit packed red cells or 25 grams albumin

^{*} Recommended Furosemide dosing = begin with 20 mg bolus or 3 mg / hr infusion or last known effective dose. Double each subsequent dose until goal achieved (oliguria reversal or intravascular pressure target) or maximum infusion rate of 24 mg / hr or 160 mg bolus reached. Do not exceed 620 mg / day. Also, if patient has heart failure, consider treatment with dobutamine.

I Genetic Testing

Portions of the blood specimens as specified in this protocol will be used for genetic analyses either for beta-receptor polymorphisms as part of an ancillary study, or for future genetic studies of ARDS that are presently undefined. ALI is a complex inflammatory condition of the lungs, and many of the inflammatory pathways thought to be involved in lung injury are associated with genetic polymorphisms. It is likely that there are, as yet undetermined, important gene/environment interactions that impact on clinical outcome. Thus it is important to collect and store DNA from large, carefully described cohorts of patients with ALI to facilitate discovery in this field with the aim to better understand the pathogenesis of ARDS and how treatment may be tailored to individual patient needs.

Genetic analysis will involve, in part, the analysis of genomic DNA and will attempt to link genotypic information to the extensive phenotypic information measured as part of this study. A layered informed consent will be used to obtain the study subjects' consent for genetic testing as follows: 1) consent for genetic studies related to ARDS, or; 2) consent for future studies not necessarily related to ARDS. The level of consent for testing (e.g. none, for ARDS studies, for future studies, or all studies) will be recorded in the Case Report Forms and stored in the Clinical Coordinating Center Data Base. All patients who recover decision-making capacity will be approached for written re-consent for genetic testing.

Two 7.5 ml EDTA plastic monovette tubes will be used to collect up to 10 ml of blood on each patient with consent for genetic testing. Samples will be labeled with pre-printed label with the subjects ARDSNet study number. DNA extraction will be done centrally.

Following extraction, DNA will be sent to a central repository to be stored (as described below). DNA will first be stored the extraction laboratory for seven years and then shipped to the central repository. Random number will identify samples during shipment, extraction, and storage in the central repository. In the future, when approved studies for genetic testing are received at the CCC, the CCC will identify samples that have the necessary level of informed consent for genetic testing. The CCC will then instruct the repository to prepare the appropriate samples for shipment. The key relating the ARDSNet study number to the specimen number will be kept at the CCC in a locked file. The CCC does not record nor store unique patient identifiers (such as initials, date of birth, hospital record numbers, addresses, phone numbers, etc.) in the data base. All data released by the CCC for genetic studies will be linked to the specimen but will be deidentified. The link (key) between the de-identified database and the patient will be removed two years after the primary publication.

Should patients or surrogates revoke their consent for genetic testing, the clinical sites will notify the CCC. The CCC will then contact the repository and request that all samples collected for genetic analysis for that patient be destroyed. Confirmation of destruction of samples will be sent to the CCC and forwarded to the clinical site.

J De-identified Data Elements for Screened, Non-Enrolled Subjects

- Was onset of ALI acute?
- Did frontal CXR show bilateral infiltrates consistent with pulmonary edema?
- Number of quadrants with opacities?
- Is patient intubated?
- PaO2
- FiO2
- Was there evidence of left atrial hypertension?
- Month of the year that patient met screening criteria (1-12).
- Gender
- Ethnicity
- Age (if age >89, 89 will be entered for age)
- Patient location (e.g. MICU, SICU, etc.) and if regularly screened
- Reason(s) patient excluded from study.
- If not excluded, not enrolled, why?
- Lung injury category (e.g. sepsis, pneumonia)
- If lung injury category=sepsis, site of infection

K Long Term Outcomes

K.1 Phone Surveys for Survivors from All 12 ARDSNet Study Sites

Table 1 summarizes the proposed measurement instruments and their rationale for each of the outcome domains evaluated in the phone-based assessments of ALI survivors from all ARDSNet study sites. These domains and instruments were determined based on a comprehensive assessment performed by the ARDSNet Long-Term Outcomes Committee and by the investigators for this proposed study.

Table 1. Phone assessments of ALI survivors from all 12 ARDSNet study sites at 6 and 12 months

Outcome Domain	Instrument	Rationale	No. of items; Time Req'd; Scale
Mortality	Custom (date & cause of death)*	- Used in existing long-term ALI study (2)	3 item; <1 min.
Physical function	Functional Performance Inventory - Short Form (FPI-SF)	-Developed in chronic pulmonary patients -Comprehensive, reliable and valid (11;12)	32 items; 5 minutes; Continuous
Mental health			
a) Depression & General Anxiety	Hospital anxiety & depression (HAD) scale (13)	-Most widely used survey in medical patients(14) -Separate subscale for depression & anxiety -Reliable and validated in medical patients (14) -Highly correlated with psychiatric evaluation (13;15)	14 items; 5 minutes (2) Continuous
b) Post-traumatic stress disorder	Impact of Events Scale – Revised (IES-R) (16)	-IES is the most commonly used instrument for assessing PTSD in the ICU (15) -Revised version (IES-R) follows DSM-IV (17) criteria -Reliable and valid (16;18)	22 items; 3 minutes (2) Continuous
Cognitive status	Telephone Mini-Mental State Examination (TMMSE) (19;20)	-MMSE is the most widely used instrument -TMMSE is designed specifically for phone use -Reliable and valid (19;20)	16 items; 5 minutes; Continuous
Health-related quality	of life		
	1. SF-36 version 2 (21)	-Most widely used instrument, esp in ALI (1-3;6-7) -Reliable and validated in ICU patients (23) -US population norms available (21)	36 items; 6 minutes; Continuous
a) Generic	2. EQ-5D (EuroQOL) (22)	-Feasible for patients with inattention& fatigue (6;22) -Recommended for use in ICU patients (5) -Provides utility estimate with US norms (24)	6 items; 2 minutes (2) Continuous
b) Fatigue	Functional Assessment of Chronic Illness Therapy (FACIT)	-Designed for patients with chronic illness -Assesses both functional & emotional impact (25;26) -Reliable and validated (27;28)	13 items; 3 minutes (25) Continuous
Return to work	Custom instrument	-Developed & used in large cohort of ALI survivors (2)	12 item; 2 min. Categorical
Health care utilization	University of Toronto ARDS Outcome study instrument (4)	-Developed and used in large longitudinal cohort of ALI survivors (4)	27 items; 8 minutes; Continuous

^{*} Also will be determined from a National Death Index via participant's Social Security Number.

Administration of phone surveys will be centralized at 2 sites: Johns Hopkins and LDS Hospital, where the 2 Principal Investigators are affiliated. Being in different time zones, this 2-site approach will allow flexibility in accessing patients across the US while also concentrating our oversight activities. Manuals of Operations will be used for training, reference and quality assurance review.

NOTES:

- (1) Estimated time for completion. This was based on pilot testing, published estimates and the experience of the ARDS Network investigators. The full telephone interview will be piloted prior to implementation.
- (2) Return to Work assessment. There are no pre-existing comprehensive survey instruments for measuring return to work and work disability in patients with lung disease. We derived our custom-made instrument from an approach used by one member of the Long-term Outcomes Committee ([name] and colleagues) to measure work disability in asthma and COPD.

K.2 Statistical Considerations for Long Term Outcomes

A number of dichotomous and continuous measures of long-term efficacy of the treatment will be analyzed.

Dichotomous measures:

- 1) Survival times will be compared for the treatment arms using log rank test.
- 2) Proportions of patients alive without major disabilities will be compared between the treatment arms using Cochran-Mantel-Haenszel test. Major disability is defined for surviving patients that are prevented from working due to a respiratory condition.
- 3) Proportions of patients alive without disability in activities of daily living (ADL) or instrumental activities of daily living (IADL) will be compared across treatment arms using Cochran-Mantel-Haenzsel test. Major disability ADL and IADL are defined based on functional performance inventory for a patient who has at least one activity in the "body care" and "maintaining household" subscales, respectively, that s/he cannot perform at all due to health reasons or does it with much difficulty.

Each of the comparisons will be done based on the data collected at 6 months, and 1-year follow up times.

Continuous measures:

- 1) Primary measure of disability defined by functional performance inventory.
- 2) Eight subscales and two summary measures of the SF-36 instrument
- 3) Depression measure defined by Beck Depression Inventory II
- 4) Cognitive measure

Continuous measures will be analyzed using analysis of variance stratified by the treatment arm.

Each of the comparisons we will be done based on the data collected at 6 months, and at 12 months follow up times. We will compare the raw continuous measures in the groups of

patients available for the follow up. There is a concern that those patients that survive and are contactable to obtain information will potentially belong to different populations for different treatment arms. If true, this will make comparison between the treatment arms no longer randomized. To address this we will compare the treatment arms using survival average causal effect (SACE). This method (Hayden 2005) uses concepts of casual inference by adjusting the estimates of the population parameters based on the model covariates. First the expected probabilities of survival and ability to contact and obtain information from a patient are computed using logistic regression. Then estimates are weighted by these computed survival and contactability to correct for potential differences in the patient populations across treatment arms selected by survival and contactability of patients. The model depends on the assumption that conditional on the values of the covariates the probabilities of a patient surviving and being contactable are independent across treatment arms. The effects of this assumption will be evaluated via a sensitivity analysis.

K.3 Citations for M1 (Choice of survey instruments)

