• **Titles:** Prospective, Randomized, Multi-center Trial of Initial Trophic Enteral Feeding Followed by Advancement to Full-calorie Enteral Feeding vs. Early Advancement to Full-calorie Enteral Feeding in Patients with Acute Lung Injury (ALI) or Acute Respiratory Distress Syndrome (ARDS)

• Objectives:

 To assess the safety and efficacy of initial trophic enteral feeding followed by advancement to full-calorie enteral feeding vs. initial advancement to full-calorie enteral feeding management strategies in reducing mortality and morbidity in patients with ALI or ARDS

• Hypotheses:

- 1. Initial trophic feeding followed by full-calorie enteral feeding will improve clinical outcomes (specifically increase the number of ventilator-free days to day 28 and decrease the 60-day, hospital mortality) in patients with ALI or ARDS by reducing systemic inflammation and the number of feeding complications as compared to early, full-calorie enteral feeding.
- **Study Design:** Multi-center, prospective, randomized, controlled clinical trials.
 - 1. A maximum of 1000 patients will be enrolled.
 - 2. Patients randomized to trophic enteral feeds will receive trophic feeding rates (20 kcal / hr) for 144 hours prior to being advanced to full-calorie feeding rates which will continue for the duration of mechanical ventilation up to study day 28.
 - 3. Patients randomized to full-calorie enteral feeds will be advanced to full-calorie feeding rates on initiation of feeding and will continue to receive full-calorie feeds for the duration of mechanical ventilation up to study day 28.
 - 4. Patients will be followed to the earlier of 60 days or hospital discharge. In addition, vital status will be ascertained at 90 days.

• Sample Size/Interim Monitoring:

This study compares the use of initial trophic enteral feeds followed by advancement to full-calorie enteral feeds versus initial full-calorie feeds in patients with ALI or ARDS. The trial will accrue a maximum of 1000 patients providing about 500 patients treated initially with trophic enteral feeds to be compared against about 500 patients treated initially with full-calorie enteral feeds. This provides 90 % power to detect an absolute difference of 2.25 ventilator-free days assuming a mean of 14 and standard deviation of 10.5 ventilator-free days (data from FACTT study) using a two sided p = 0.05 significance level.

- 2 The principal analysis will be intent-to-treat, based upon randomization assignment.

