4.6 Randomization

After obtaining a signed and dated informed consent, the coordinating center will be called and an assignment, in the form of a study ID number, will be made by computer-generated randomization to initial trophic or initial full feedings.

Randomization will be accomplished with a web based randomization system. Each research coordinator will have a unique Personal Identification Number (PIN). The randomization will indicate to study personnel whether the patient is to receive initial trophic or initial full feedings.

The randomization will be stratified by institution, and by shock at study entry to one of the two study arms.

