6.6 Endpoint Determinations

- 1. Vital status at 28, 60, and 90 days until discharged home on UAB.
- 2. Time of initiation of unassisted breathing (assuming patient achieves 48 consecutive hours of unassisted breathing)
- 3. Need for re-instituting assisted or mechanical ventilation after achieving 48 consecutive hours of unassisted breathing
- 4. Status 48 hours after initiation of unassisted breathing
- 5. Date of ICU discharge
- 6. Date of Hospital discharge

7 Statistical Considerations

Primary Endpoint

The primary endpoint will be ventilator free days. All analyses will be intent to treat. A three-way analysis of variance will be used with factors shown in Table 1. The primary model will be a main effects model. The primary comparisons will be whether initial trophic feeding followed by full-calorie enteral feeding is different than initial advancement to full-calorie enteral feeding.

Table 1: Factorial Design

Factor	Level
	1. Omega-3 Fatty Acid, Gamma-linolenic acid (GLA), and anti-
Nutriceutical (Medical Food)	oxidant supplementation
	2. Placebo
	3. None
Time of Feeding	1. Initial trophic feeding followed by full-calorie enteral feeding
Time of Feeding	2. Initial advancement to full-calorie enteral feeding
Shock at baseline	1. Yes
Shock at baseline	2. No

The maximum sample size will be 1000 patients. The study will be monitored using a flexible group sequential design that stops for efficacy/futility. Since trophic vs. full-calorie feeding is a two-sided question with either strategy possibly improving outcomes, efficacy and futility stopping rules will be the same (i.e. efficacy of one strategy would be the same as futility of the other strategy). The reported confidence intervals on the treatment difference will be adjusted for the group sequential design using the method of Jennison & Turnbull.

In order to allow flexibility we will use alpha and beta spending boundaries as described by DeMets and Ware (zl=2.277,delta=1.663,zu=2.025,m=4, mu=3.3837) (DeMets, 1982). Trophic vs. full-calorie feeding is a two sided question which will have a two-sided efficacy boundary and an inner wedge futility boundary that will be formed by reflecting the lower futility boundary about the abscissa. There would be no chance of futility stopping of two sided factors at the first look.

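### Appendix K.2 gives treatment arm the role of a stratum in the ANOVA of the continuous long-term outcomes; it should be the tested factor, alongside the shock and nutriceutical factors of section 7

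*Protocol*

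**What the plan says.** Appendix K.2 lists four groups of continuous long-term measures: functional performance, SF-36 subscales and summaries, depression, and cognition. The ANOVA for them is set out in one sentence: "Continuous measures will be analyzed using analysis of variance stratified by the treatment arm". The section then turns to comparisons at 6 and 12 months. It begins a sentence with "We will compare the raw continuous measures in the groups of" and completes it with the patients who can be followed up. Because survivors who can be reached may differ between arms, it adds a second analysis: "To address this we will compare the treatment arms using survival average causal effect (SACE".

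For the dichotomous measures, K.2 says: "Proportions of patients alive without major disabilities will be compared between the treatment arms using Cochran-Mantel-Haenszel test". It names no strata for that test.

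Two other sections bear on this. Section 4.6 states: "The randomization will be stratified by institution, and by shock at study entry to one of the two study arms". Section 7 states, for the primary endpoint: "A three-way analysis of variance will be used with factors shown in Table 1". That table has three factors: nutriceutical, time of feeding (the treatment) and shock at baseline. Institution is not among them.

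**The concern.** In a stratified analysis the stratum is held fixed and comparisons are made within it. If arm is the stratum, the difference between arms is absorbed by the stratum terms and is not tested, and the K.2 sentence names no other factor to test. So the ANOVA as worded does not deliver the comparison that the next lines of the same section promise.

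The natural repair is to read the sentence as an ANOVA on arm alone. That gives a valid comparison, but a different model from section 7, where treatment is a factor next to shock and nutriceutical. It also leaves out shock, although randomization is balanced on it. At stake are the precision of the long-term functional, quality-of-life, depression and cognitive comparisons, and a protocol sentence that an analyst would have either to copy or to contradict.

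**Working it through.** K.2 gives no sample size, power or alpha for these outcomes, so there is no figure to reproduce. The check has two parts.

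**1. The texts side by side**

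| Place | Role of treatment | Shock | Nutriceutical | Institution |
|---|---|---|---|---|
| Section 4.6, randomization | allocated | stratum | not named | stratum |
| Section 7, Table 1, primary ANOVA | factor | factor | factor | not included |
| K.2, continuous measures | stratum | not named | not named | not named |
| K.2, dichotomous measures | compared | not named | not named | not named |

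Only the K.2 sentence on continuous measures makes treatment a stratum. With a separate intercept for each arm and nothing else in the model, those intercepts carry the whole arm difference. Declaring them strata leaves nothing to test. Declaring arm a factor makes the same model estimate and test the difference.

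**2. What an arm-only ANOVA would cost**

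The inputs are assumptions, not figures from the protocol: half the patients in shock, randomization balanced within shock, total outcome SD of 1, treatment effect 0.2 SD, and shock explaining a share R² of the variance. The number of patients is 1000, the protocol's maximum enrolment. Each setting was simulated 2000 times, and both models were fitted to the same data.

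| R² | Type I error, arm only | Type I error, arm + shock | Power, arm only | Power, arm + shock | Power difference |
|---|---|---|---|---|---|
| 0 | 0.044 | 0.044 | 0.887 | 0.887 | 0 |
| 0.05 | 0.0485 | 0.053 | 0.8765 | 0.8865 | 1.0 point |
| 0.10 | 0.038 | 0.0485 | 0.8925 | 0.9145 | 2.2 points |
| 0.20 | 0.033 | 0.0545 | 0.913 | 0.9425 | about 3 points |

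The simulation standard error is √(0.05 × 0.95 / 2000) = 0.005 for a type I error near 0.05, and √(0.9 × 0.1 / 2000) = 0.007 for a power near 0.9.

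A closed form confirms the pattern. With balance on shock, the estimated difference varies with variance proportional to 1 − R², while the arm-only ANOVA computes its standard error from the full variance. Let λ = 0.2 × √1000 / 2 = 3.162 and s = √(1 − R²), with critical value 1.962.

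- Type I error, arm only: 2Φ(−1.962 / s). For R² = 0.05, 0.10 and 0.20, s = 0.975, 0.949 and 0.894, giving 0.044, 0.039 and 0.028.
- Power, arm only: Φ((λ − 1.962) / s) = 0.891, 0.897 and 0.910.
- Power, adjusted: Φ(λ / s − 1.962) = 0.900, 0.915 and 0.942.
- Difference: 0.9, 1.8 and 3.2 points.

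The power loss depends on the number analysed. Only survivors who can be reached contribute. If the 25.4% 90-day hospital mortality in section 7, Table 3 is taken as the loss, at most 1000 × (1 − 0.254) = 746 remain. Then λ = 0.2 × √746 / 2 = 2.731, and the same formulas give differences of 1.5, 2.9 and 5.7 points. This assumes that the balance on shock roughly carries over to survivors. The type I error is unchanged.

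**The case against.** The strongest reply is that the section answers the point itself. K.2 presents these outcomes as evidence on the efficacy of treatment, compares the raw measures between the groups, and adds a separate between-arm analysis by survival average causal effect. This stands. A reader might infer from the ANOVA sentence that the plan contains no between-arm test or estimate for the long-term outcomes. The documents do not support that inference, because the comparison is clearly intended and one version of it is stated independently of the ANOVA.

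A second reply is that covariates and strata are details for a statistical analysis plan, which is not at hand. This stands in part. Leaving the Cochran-Mantel-Haenszel strata unnamed, or a covariate unlisted, would not be a fault by itself. But K.2 does state a model and gives the treatment variable the wrong role in it, which is a misstatement and not a gap.

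A third reply is that the precision argument rests on assumed variance shares, and that leaving out a stratum does not harm validity. Both are correct. A reader might also infer that the long-term analysis must adjust for institution in order to match section 7. It need not: institution is a randomization stratum in section 4.6, but the primary ANOVA does not include it.

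**Conclusion.** The K.2 sentence is wrong as written and should be corrected: treatment arm is named as the stratum where it should be the tested factor. This is a drafting error in the model sentence. Under the reasonable arm-only reading the analysis is valid and slightly conservative. It departs from the section 7 model and loses a little precision to the extent that shock predicts outcome: about 1-3 points of power at 1000 patients and a 0.2 SD effect, if shock explains 5-20% of the variance, and somewhat more with fewer patients. The type I error is not inflated. No figure in the protocol supports any particular variance share, and if shock explains nothing, nothing is lost. Severity is minor. The primary endpoint, sample size, alpha and stopping boundaries are unaffected.

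**What to change.** Replace the K.2 sentence on continuous measures with wording such as: *analysis of variance with treatment arm as the tested factor, adjusted for shock at baseline and the nutriceutical factor as in section 7, Table 1*. The nutriceutical term belongs there because, according to section 4.1, the first 272 patients were enrolled in the factorial design. State in the same place that the Cochran-Mantel-Haenszel tests are stratified by shock at baseline. Adjustment for institution is optional. If it is wanted, justify it by the randomization in section 4.6 and do not describe it as matching section 7. The change costs one or two sentences and needs no new data, since shock and assignment are already recorded at randomization.
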